3.6. Dose Escalation

In Part A, doses will be administered in an escalating manner following satisfactory review by the Sponsor and Investigator of the safety, and tolerability data up to Day 10 (216 hours postdose) from groups that received lower doses of OLP-1002. For escalation to doses > 12 µg, PK data up to Day 7 (144 hours postdose) will also be reviewed. All available safety, tolerability, and PK data from previous groups will be reviewed prior to dose escalation.

In Part B, doses will be administered in an escalating manner following satisfactory review of safety, tolerability, and PK data up to Day 22 (216 hours post-final dose) from groups that received lower doses of OLP-1002. Doses may be reduced and may be lower than the starting dose. Available safety, tolerability, and PK data from all previous groups will be reviewed prior to dose escalation.

Dose escalation in Part A will only occur if data from a minimum of 4 subjects (Groups A1, A3, A5, A7, and A8) or 6 subjects (Groups A2, A4, and A6) have been reviewed from the previous lower dose group, such that data from a minimum of 3 or 4 subjects, respectively, who have received OLP-1002 will be used to make the dose-escalation decision. Dose escalation in Part B will only occur if data from a minimum of 6 subjects have been reviewed from the previous lower dose group, such that data from a minimum of 4 subjects who have received OLP-1002 will be used to make the dose-escalation decision.

The justification for this is as follows:

- The study drug is of a known pharmacological class for which the on-target effects in humans are well characterized. Based upon nonclinical data, no clinically important off-target effects are expected within the proposed dose range.

- A minimum of 3 subjects receiving the active drug is considered sufficient to characterize the safety profile for OLP-1002.

Between each dose escalation, the Investigator will review all available blinded data to ensure it is safe to proceed with the planned dose escalation. An interim safety report, summarizing results from all available safety assessments, will be sent to the Sponsor and a dose-escalation meeting will occur prior to the start of each successive group. Any clinically significant results will be discussed with the Sponsor before dose escalation continues. Interim PD data may also be reviewed on an ongoing basis. In the event of a disagreement between Sponsor and Investigator on the dose-escalation decision, the decision of the Investigator will be upheld.

3.7. Dose Escalation Stopping Criteria

In Parts A and B, following consultation with the Sponsor, dose escalation will be stopped if:

- Clinically relevant signs or symptoms of similar nature occur in 2 or more subjects in a group that, in the opinion of the Investigator, warrant stopping of dose escalation.
- One or more subjects experience an SAE that is considered to be related to OLP-1002.
- Two or more subjects in the same group experience severe non-serious AEs (ie. severe non-serious AEs considered as, at least, possibly related to OLP-1002 administration), independent of whether the AEs are within or not within the same system organ class.
- There is evidence of clinically significant increases in aspartate aminotransferase, alanine aminotransferase or alkaline phosphatase (defined as 3 times the upper limit of normal), or total bilirubin (defined as 2 times the upper limit of normal) that are considered to be related to OLP-1002 in 2 or more subjects in a group. Results will be confirmed with repeat testing.
- QT interval corrected for heart rate using Fridericia's method (QTcF) increases > 60 msec compared to baseline (predose for Part A or Day 1 predose for Part B) and/or absolute QTcF values > 500 msec (confirmed by repeat measurement) in 2 or more subjects in a group.
- Tachycardia (> 150 beats/min) in the resting supine position (confirmed by 2 repeat measurements) on at least 1 occasion within a 24-hour interval in ≥ 1 subject in a group.
- Severe hypertension (systolic blood pressure > 180 mmHg and/or diastolic blood pressure > 110 mmHg) in the resting supine position (confirmed by 2 repeat measurements) on at least 1 occasion within a 24-hour interval in ≥ 1 subject in a group.
- The dose will not exceed 20 μg or the systemic exposure for any individual subject is predicted to exceed a C_{max} of 24.9 ng/mL (plasma) and/or an AUC_{0-24} of 128 ng/mL; i.e., systemic exposure will be no greater than the NOAEL in the most sensitive species (100,000 pmol/kg in rat [462 $\mu\text{g}/\text{kg}$]).

If the sponsor deems it appropriate to resume dosing after the internal safety review, it can be done after the approval of a substantial protocol amendment.

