4.4. Subject Withdrawal and Replacement

A subject is free to withdraw from the study at any time. In addition, a subject will be withdrawn if any of the following criteria are met:

- noncompliance with the study restrictions that might affect subject safety or study assessments/objectives, as considered applicable by the Investigator (or designee)
- any clinically relevant sign or symptom that, in the opinion of the Investigator (or designee), warrants subject withdrawal, including:
 - a serious adverse reaction (i.e., a SAE considered at least possibly related to OLP-1002 administration),
 - severe non-serious adverse reaction (i.e., severe non-serious AE considered to at least possibly related to OLP-1002 administration),
 - elevated AST, ALT, ALK (3 x ULN) or total bilirubin (2 x ULN),
 - QTcF increases > 60 msec compared to baseline (predose for Part A or Day 1 predose for Part B) and/or absolute QTcF values > 500 msec (confirmed by repeat measurement),
 - Tachycardia (> 150 beats/min) in the resting supine position (confirmed by 2 repeat measurements),
 - Severe hypertension (systolic blood pressure > 180 mmHg and/or diastolic blood pressure > 110 mmHg) in the resting supine position (confirmed by 2 repeat measurements).

If a subject is withdrawn, the Sponsor will be notified and the date and reason(s) for the withdrawal will be documented in the subject's electronic Case Report Form (eCRF). If a subject is withdrawn, efforts will be made to perform all follow-up assessments, if possible ([Appendix 6](#)). Other procedures may be performed at the Investigator's (or designee's) and/or Sponsor's discretion. If the subject is in-house, these procedures should be performed before the subject is discharged from the clinic. The Investigator (or designee) may also request that the subject return for an additional Follow-up visit. All withdrawn subjects will be followed until resolution of all their AEs or until the unresolved AEs are judged by the Investigator (or designee) to have stabilized.

Subjects who are withdrawn for reasons not related to study drug may be replaced following discussion between the Investigator and the Sponsor. Subjects withdrawn as a result of AEs thought to be related to the study drug will generally not be replaced.

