5.4. Blinding

The following controls will be employed to maintain the double-blind status of the study:

- The placebo solution will be identical in appearance to the OLP-1002.
- The Investigator and other members of staff involved with the study will remain blinded to the treatment randomization code during the assembly procedure.

To maintain the blind, the Investigator will be provided with sealed randomization code-break envelopes for each subject, containing details of their treatment. These individual sealed envelopes will be kept in a limited access area that is accessible 24 hours a day. In order to manage subject safety or to support dose-escalation decisions (in the event of possibly treatment-related SAEs or severe AEs), the decision to unblind resides solely with the Investigator. Whenever possible, and providing it does not interfere with or delay any decision in the best interest of the subject, the Investigator will discuss the intended code-break with the Sponsor. If it becomes necessary to break the code during the study, the date, time, and reason will be recorded in the subject's source data and on the individual envelope and will be witnessed by a second person.

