10. APPENDICES

Appendix 1: Adverse Event Reporting

Definitions

An adverse event (AE) is any untoward medical occurrence in a patient or clinical investigation subject administered a pharmaceutical product, which does not necessarily have a causal relationship with this treatment. An AE can therefore be any unfavorable and/or unintended sign (including a clinically significant abnormal laboratory finding), symptom, or disease temporally associated with the use of a study drug, whether or not related to the study drug.

Assessment of Severity

The Investigator will be asked to provide an assessment of the severity of the AE using the following categories:

- **Mild:** Usually transient and may require only minimal treatment or therapeutic intervention. The event does not generally interfere with usual activities of daily living.
- **Moderate:** Usually alleviated with additional specific therapeutic intervention. The event interferes with usual activities of daily living, causing discomfort but posing no significant or permanent risk of harm to the subject.
- **Severe:** Interrupts usual activities of daily living, or significantly affects clinical status, or may require intensive therapeutic intervention.

Relationship to Study Treatment

The Investigator (or designee) will make a determination of the relationship of the AE to the study drug using a 4-category system according to the following guidelines:

- **Not Related:** The AE is definitely caused by the subject's clinical state or the study procedure/conditions.
- **Unlikely Related:** The temporal association between the AE and the drug is such that the drug is not likely to have any reasonable association with the AE.
- **Possibly Related:** The AE follows a reasonable temporal sequence from the time of drug administration but could have been produced by the subject's clinical state or the study procedures/conditions.
- **Related:** The AE follows a reasonable temporal sequence from administration of the drug, abates upon discontinuation of the drug, follows a known or hypothesized cause-effect relationship, and (if appropriate) reappears when the drug is reintroduced.

Follow-up of Adverse Events

Every reasonable effort will be made to follow up with subjects who have AEs. Any subject who has an ongoing AE that is possibly related or related to the investigational medicinal product (IMP) or study procedures at the Follow-up visit will be followed up, where possible,

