until resolution or until the unresolved AE is judged by the Investigator (or designee) to have stabilized. This will be completed at the Investigator's (or designee's) discretion. Any subject who has an ongoing AE that is not related or unlikely related to the IMP or study procedures at the Follow-up visit can be closed out as ongoing at the Investigator's discretion.

Adverse Drug Reactions

All noxious and unintended responses to an IMP (ie, where a causal relationship between an IMP and an AE is at least a reasonable possibility) related to any dose should be considered adverse drug reactions.

For marketed medicinal products, a response to a drug which is noxious and unintended and which occurs at doses normally used in man for prophylaxis, diagnosis, or therapy of diseases or for modification of physiological function is to be considered an adverse drug reaction.

An unexpected adverse drug reaction is defined as an adverse reaction, the nature or severity of which is not consistent with the applicable product information (eg, Investigator's Brochure for an unapproved IMP).

Serious Adverse Events

A serious AE (SAE) is defined as any untoward medical occurrence that at any dose either:

- results in death
- is life-threatening
- requires inpatient hospitalization or prolongation of existing hospitalization
- results in persistent or significant disability/incapacity (disability is defined as a substantial disruption of a person's ability to conduct normal life functions)
- results in a congenital anomaly/birth defect
- results in an important medical event (see below).

Important medical events that may not result in death, be life-threatening, or require hospitalization may be considered SAEs when, based upon appropriate medical judgment, they may jeopardize the subject and may require medical or surgical intervention to prevent one of the outcomes listed in this definition.

Instances of death or congenital abnormality, if brought to the attention of the Investigator at any time after cessation of the study treatment and considered by the Investigator to be possibly related to the study treatment, will be reported to the Sponsor.

Definition of Life-threatening

An AE is life-threatening if the subject was at immediate risk of death from the event as it occurred (ie, does not include a reaction that might have caused death if it had occurred in a more serious form). For instance, drug-induced hepatitis that resolved without evidence of

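### The Section 3.7 SAE stopping bullet asks for 'related' where the severe-AE bullet, Section 4.4 and Section 5.4 ask only for 'possibly related', so SAEs rated Possibly Related do not trigger the pre-set stop

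*Protocol*

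**What the plan says.** Section 3.7 lists the events that stop dose escalation in Parts A and B. Three of its bullets set a causality level:

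- **SAEs:** "One or more subjects experience an SAE that is considered to be related to OLP-1002". One subject is enough, and the bullet is not confined to a single group.
- **Severe non-serious AEs:** two or more subjects in the same group, counting "severe non-serious AEs considered as, at least, possibly related to OLP-1002 administration", whatever the system organ class.
- **Liver tests:** two or more subjects in a group, with the increases considered related to OLP-1002.

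After a stop, if the sponsor wishes to resume dosing, "it can be done after the approval of a substantial protocol amendment".

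Section 4.4 includes among the reasons for withdrawing a subject "a serious adverse reaction (i.e., a SAE considered at least possibly related to OLP-1002 administration") and, for less serious events, a "severe non-serious AE considered to at least possibly related to OLP-1002 administration". Section 5.4 lets the Investigator break the code to manage subject safety or "to support dose-escalation decisions (in the event of possibly treatment-related SAEs or severe AEs").

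Appendix 1 defines four causality ratings: Not Related, Unlikely Related, Possibly Related and Related. Possibly Related reads in part "The AE follows a reasonable temporal sequence from the time of drug administration but could have been produced by"; the alternative causes it then names are clinical state and study procedures or conditions. Related is a separate rating that also asks for abatement once the drug is stopped and a known or hypothesized mechanism. The same appendix sets the general standard for an adverse drug reaction at the lower level: "where a causal relationship between an IMP and an AE is at least a reasonable possibility".

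**The concern.** The rules for subject withdrawal, for code-break and for stopping on severe non-serious AEs all act at the 'possibly' level. The rule for stopping on SAEs, the graver class, uses a word that Appendix 1 reserves for a stronger rating. An SAE rated Possibly Related is therefore a ground for withdrawing the subject and a reason to consider unblinding, but it does not by itself meet the SAE stop.

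This is a first-in-human study in healthy volunteers. Part A is single-dose, so withdrawing an affected subject spares that subject no further dosing. The escalation rule is what protects the next group. At stake is whether an SAE that may be due to the drug leads to a pre-set halt, lifted only by an approved amendment, or to a case-by-case judgement.

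**Working it through.** No sample size, power or error rate is involved. The check sets the rules side by side and traces events through them.

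**Step 1. Causality level by rule**

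| Rule | Event | Level | Count |
|---|---|---|---|
| 3.7 | SAE | related | 1 subject |
| 3.7 | severe non-serious AE | at least possibly related | 2 in same group |
| 3.7 | liver tests | related | 2 in a group |
| 4.4 | SAE | at least possibly related | the subject concerned |
| 4.4 | severe non-serious AE | at least possibly related | the subject concerned |
| 5.4 | SAE or severe AE | possibly related | the subject concerned |

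Four of the six act at the 'possibly' level. Two, the SAE stop and the liver stop, do not.

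**Step 2. Map to Appendix 1.** Taken literally, the SAE bullet covers one of the four ratings (Related). The severe non-serious AE bullet covers two (Possibly Related and Related).

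**Step 3. One SAE rated Possibly Related, in one subject**

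- Section 4.4: a listed ground for withdrawal, under a lead-in that refers to the Investigator's opinion.
- Section 5.4: code-break is available.
- Section 3.7 SAE bullet: not met, because the rating is not Related.
- Section 3.7 severe-AE bullet: not met, because it is limited to non-serious events and needs two subjects.
- Section 3.7 signs-and-symptoms bullet: not met, because it needs two subjects.
- Other Section 3.7 bullets: met only if the event also satisfies them, for example confirmed tachycardia above 150 beats/min or confirmed severe hypertension in one subject.

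**Step 4. Two subjects in one group**

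- Two Possibly Related severe non-serious AEs of different nature: escalation stops.
- Two Possibly Related SAEs of different nature: neither adverse-event bullet is met. The signs-and-symptoms bullet is not met either, since it requires a similar nature and the Investigator's opinion that stopping is warranted.

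**Step 5. The comparison that runs the other way**

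- One Related SAE: escalation stops.
- One Related severe non-serious AE: escalation does not stop.

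The SAE bullet is thus stricter on count and scope, and laxer on causality alone.

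**Step 6. How reachable is 'Related'?** Read literally, its definition is hard to satisfy in Part A, where there is no continuing dosing to discontinue. It is harder still for an SAE that is fatal or permanently disabling, which cannot abate, or one with no hypothesized mechanism. Such events would tend to be rated Possibly Related.

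**The case against.** The strongest reply is that the SAE bullet uses 'related' in lower case, does not cite the Appendix 1 rating, and may simply mean drug-related in the ordinary sense. Section 4.4 uses similar loose wording when it discusses replacement of withdrawn subjects. Appendix 7 records that the SAE criteria in Sections 3.7 and 4.4 came in together under Amendment 1, which suggests one intended threshold. That is fair as to intent. It does not settle the reading, because the very next bullet spells out the 'possibly' level and Appendix 1 separates the two ratings. Two readers could act differently on the same SAE.

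A lower threshold for withdrawing one subject or breaking one code than for halting escalation is also defensible in itself. That explains the difference from Sections 4.4 and 5.4. It does not explain the difference from the severe-AE bullet, which is itself a stopping rule.

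Three stronger readings are tempting, and the documents do not support them:

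- *That the SAE rule is weaker overall than the severe-AE rule.* It is not: it acts on one subject rather than two in the same group.
- *That the SAE bullet is the lone outlier among the stopping criteria.* Of the three Section 3.7 bullets that set a causality level, two say 'related', the liver bullet being the other.
- *That escalation would go ahead after a Possibly Related SAE.* Section 3.6 requires a satisfactory review and a dose-escalation meeting before each new group, clinically significant results must be discussed first, and the Investigator prevails in a disagreement. Section 4.5 also allows the study to be discontinued. Even the Section 3.7 stop follows consultation with the Sponsor and depends on the Investigator's own causality rating.

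These points narrow the practical gap. They do not remove the mismatch.

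**Conclusion.** The point holds as a mismatch in causality threshold. One or more SAEs rated Possibly Related do not trigger the pre-set stop, or the amendment needed before resuming, unless another bullet happens to be met. Under the two adverse-event bullets, two subjects in a group suffice for Possibly Related severe non-serious AEs, while no number suffices for Possibly Related SAEs. Holding escalation then rests on the Section 3.6 review and the Investigator's judgement. Protection is weakened in form, not absent.

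The conclusion assumes that 'related' in Section 3.7 carries its Appendix 1 meaning, which is the likelier reading but not the only one. It uses no assumed event rates. It is worth correcting because the study is first-in-human in healthy volunteers and one phrase closes the gap.

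**What to change.** Reword the second bullet of Section 3.7 to: *One or more subjects experience an SAE considered at least possibly related to OLP-1002.* This matches Section 4.4's own definition of a serious adverse reaction. Add that an SAE in a subject shown by Section 5.4 code-break to have received placebo does not count. The liver bullet carries the same 'related' wording and can be considered in the same edit.

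The cost is real but limited. A single SAE that the clinical state or study procedures could have caused may halt escalation until a substantial amendment is approved by the ethics committee and, as locally required, the regulator. Code-break relieves this only in part. Placebo is 1 of 4 subjects or 2 of 8 in a group, and 1/4 = 2/8 = 25%. For an SAE unrelated to treatment, code-break would therefore lift the stop in about 25% of cases and leave it standing in about 75%.

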4. SELECTION OF STUDY POPULATION

4.1. Inclusion Criteria

Subjects must satisfy all of the following criteria at the Screening visit unless otherwise stated:

1. Healthy male or females of any race, between 18 and 60 years of age, inclusive.
2. Body mass index (BMI) between 18.0 and 28.0 kg/m², inclusive.
3. In good health, determined by no clinically significant findings from medical history, physical examination, single 12-lead ECG (resting heart rate > 45 bpm and < 90 bpm), vital signs measurements, and clinical laboratory evaluations (congenital nonhemolytic hyperbilirubinemia [eg, suspicion of Gilbert's syndrome based on total and direct bilirubin] is not acceptable) at Screening as assessed by the Investigator (or designee).
4. Willing to abide by the contraception requirements as detailed in [Appendix 4](#).
5. Able to comprehend and willing to sign an ICF and to abide by the study restrictions.

4.2. Exclusion Criteria

Subjects will be excluded from the study if they satisfy any of the following criteria at the Screening visit unless otherwise stated:

1. Significant history or clinical manifestation of any metabolic, allergic, dermatological, hepatic, renal, hematological, pulmonary, cardiovascular, gastrointestinal, neurological, respiratory, endocrine, or psychiatric disorder, as determined by the Investigator (or designee).
2. History of significant hypersensitivity, intolerance, or allergy to any drug compound, food, or other substance, unless approved by the Investigator (or designee).
3. Any of the following:
 - QTcF > 450 ms confirmed by repeat measurement.
 - QRS duration > 110 ms confirmed by repeat measurement.
 - PR interval > 220 ms confirmed by repeat measurement.
 - findings which would make QTc measurements difficult or QTc data uninterpretable.
 - history of additional risk factors for torsades de pointes (eg, heart failure, hypokalemia, family history of long QT syndrome).
4. Female subjects who are pregnant or breastfeeding.
5. History of alcoholism or drug/chemical abuse within 1 year prior to Screening.

6. Alcohol consumption of > 21 units per week for males and >14 units per week for females. One unit of alcohol equals ½ pint (285 mL) of beer or lager, 1 glass (125 mL) of wine, or 1/6 gill (25 mL) of spirits.
7. Positive alcohol breath test result or positive urine drug screen (confirmed by repeat) at Screening or Check-in.
8. Positive hepatitis panel and/or positive human immunodeficiency virus test ([Appendix 2](#)).
9. Active skin conditions such as dermatitis, allergy, eczema, psoriasis, or abnormal healing.
10. Tattoos, scars, or moles that in the opinion of the Investigator are likely to interfere with dosing or study assessments at any of the potential injection sites.
11. Participation in a clinical study involving administration of an investigational drug (new chemical entity) in the past 90 days or 5 half-lives of the investigational product, whichever is longer, prior to Check-in.
12. Use or intend to use any medications/products known to alter drug absorption, metabolism, or elimination processes, including St. John's wort, within 30 days prior to Check-in, unless deemed acceptable by the Investigator (or designee).
13. Use or intend to use any prescription medications/products other than hormone-replacement therapy, oral, implantable, transdermal, injectable, or intrauterine contraceptive concomitant medications within 14 days prior to Check-in, unless deemed acceptable by the Investigator (or designee).
14. Use or intend to use slow-release medications/products considered to still be active within 14 days prior to Check-in, unless deemed acceptable by the Investigator (or designee).
15. Use or intend to use any nonprescription medications/products including vitamins, minerals, and phytotherapeutic/herbal/plant-derived preparations within 7 days prior to Check-in, unless deemed acceptable by the Investigator (or designee) and/or Sponsor have given their prior consent.
16. Use of tobacco- or nicotine-containing products within 3 months prior to Check-in.
17. Receipt of blood products within 60 days prior to Check-in.
18. Donation of blood from 3 months prior to Screening, plasma from 2 weeks prior to Screening, or platelets from 6 weeks prior to Screening.
19. Poor peripheral venous access.
20. Have previously completed or withdrawn from this study or any other study investigating OLP-1002, and have previously received the investigational product.
21. Subjects who, in the opinion of the Investigator (or designee), should not participate in this study.
22. Part A – PD assessment groups only
 - Subjects considered non-acceptable responders to the intradermal capsaicin test at screening, defined as maximum VAS score of < 3.0 or > 9.0.

